5.3 Handling of Missing Data

Missing data will be minimized by rigorous follow-up and investigator and site training. Additionally, for subjects in the DTM™ SCS arm who do not have a successful Trial Phase, results from the Trial Phase will be utilized for the primary endpoint as described in Section **Error! Reference source not found..** Methods for handling missing data for primary and secondary endpoints are also described in 5.3 and 5.7.2.1. Additionally, sensitivity analyses for missing data will be performed. Unless otherwise specified, all other analyses will be based on the evaluable data with no imputation.

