Exclusion Criteria	
A subject must NOT MEET ANY of the following exclusion criteria:
 
 
1. Had previous lumbar spinal surgery (e.g., lumbar fusion, discectomy, laminectomy, laminotomy)
 
2. Has a medical, anatomical, and/or psychosocial condition that is contraindicated for commercially available Intellis™ SCS systems as determined by the Investigator
 
3. Has a diagnosed back condition with inflammatory causes of back pain (e.g., onset of severe pain with activity), serious spinal pathology and/or neurological disorders as determined by the investigator
 
4. Be concurrently participating in another clinical study
 
5. Has an existing active implanted device such as a pacemaker, another SCS unit, peripheral nerve stimulator, and/or drug delivery pump, etc.
 
6. Has a pain in other area(s) and/or medical condition requiring the regular use of significant pain medications that could interfere with accurate pain reporting, and/or confound evaluation of study endpoints, as determined by the Investigator
 
7. Has mechanical spine instability as determined by the Investigator
 
8. Has undergone, within 30 days prior to enrollment, an interventional procedure to treat back and/or leg pain, which is providing significant pain relief
 
9. Has unresolved major issues of secondary gain (e.g., social, financial, legal), as determined by the investigator
 

	
10. Be involved in an injury claim under current litigation or has a pending or approved worker's compensation claim
 
11. Be pregnant (determined by urine testing unless female subject is surgically sterile or post-menopausal. If female, sexually active, and childbearing age, subject must be willing to use a reliable form of birth control.)

Primary Endpoint	The primary efficacy endpoint is the percentage of randomized subjects who respond (a decrease in back pain VAS by at least 50% compared to baseline) to SCS therapy at 6 months (superiority analysis). Subjects who do not have a successful Trial Phase are considered failures (non-responders) toward the primary endpoint.
Secondary Endpoints & Additional Measures	Secondary endpoints of this study are to further document the safety, clinical effectiveness and health economic analytics of the DTM™ SCS delivered through IntelliS™ system when compared to CMM alone for the treatment of chronic pain of the back and limbs.

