3.2 Blinding

Due to the nature of the treatment groups, comparing an implantable medical device with conventional medical management that may involve multiple different treatments, it is not feasible to blind the subjects, implanting physicians or the clinical site personnel to the group assignments. The assessment of treatments are done by the subjects and not by the site personnel, so the lack of blinding of site personnel should not affect results as pain is the major assessment and subjects tend to describe pain truthfully since it affects their everyday life dramatically and not be influenced by knowledge of which treatment arm they are assigned to. In order to minimize potential assessment bias, the subjects will receive the standard instructions for completing the questionnaires.

4 Sample Size Determination

The clinical investigational plan requires a screening process for all subjects that provide written informed consent. These subjects will undergo screening to assess eligibility. Subjects may be excluded for various reasons during screening. Accordingly, in order to include an estimated 150 subjects to the point of randomization, up to 300 subjects may need to be consented and enrolled to account for exclusions prior to randomization.

The sample size estimate to determine primary endpoint is based on the primary objective of demonstrating superiority of the test group to the control group. Established methods were followed in determining the superiority criteria and the related sample size estimate

- Test basis: Pearson Chi-square binomial test for superiority
- Estimated responder rate of 60% in the test group and 30% in the control group
- Significance level, alpha, of 0.05 two-sided
- Randomization: 1:1

With these assumptions, a sample size of 50 subjects in each group will result in greater than 85% power for the study.

Based on the primary endpoint requirement, a minimum of 50 subjects per treatment group are required (100 total). To account for a combined estimated attrition of 33% for subjects that do not complete the Trial Phase, and subjects that exit study before the 6-month primary endpoint visit, approximately 150 subjects would need to be randomized.

To account for 50% attrition prior to randomization (including subject ineligibility after signing the informed consent and subject dropout), it is estimated that a total of up to 300 subjects would need to be enrolled in the study.

Statistical Analysis Plan		Page 7 of 14

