5.2 Analysis Sets

The following analysis sets are defined for analysis:

- Modified Intent to Treat (mITT): All randomized subjects to the test arms who successfully complete the Trial Phase and all successfully randomized subjects to the control arm.
- Intent-to-Treat (ITT): All successfully randomized subjects who met all the enrollment criteria.
- Per-Protocol (PP): All test subjects who received a permanent device implant and all control subjects who contributed their data to the primary and secondary endpoint without any major protocol deviations (that would render their data unevaluable).

The primary analysis of the primary and secondary endpoints will be performed on the mITT population. Supportive analyses will be performed for the Intent-to-Treat and Per-Protocol population.

For secondary endpoint analyses incorporating crossover data (i.e. data gathered in the post 6-month periods), sensitivity analyses will be performed to examine the impact of crossover.

If a supportive analysis set is the same as the mITT set, the results will be the same and will not be regenerated for that supportive analysis set.

Statistical Analysis Plan		Page 8 of 14
Sponsor SGX International	Study EU RCT DTM SCS vs. CMM	Version 3.0

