5.7.1.2 Handling of Missing Data

For subjects in the DTM™ SCS arm who do experience an unsuccessful Trial Phase, also referred to as a **Trial Failure**, results (i.e., VAS back scores) from the Trial Phase will be utilized for the primary endpoint. Specifically, the Trial Phase results of subjects who failed the Trial Phase will be attributed for each time point throughout the study, as if they remained in the study.

Subjects who did not complete the Trial Phase due to withdrawal (e.g., an adverse event experienced during the Trial Phase, physician withdrawal due to non-compliance, withdrawal of consent, etc.), will not be included in the mITT analysis data set.

In the event of missing primary endpoint data among the mITT subjects either randomized to control or DTM™ SCS subjects who did complete the Trial Phase, the primary analysis for the primary endpoint will be conducted using multiple imputation (MI) methodology rather than the methods specified in Section 5.7.1.1. The specified Pearson Chi-square test will be presented for the observed data as a supporting analysis.

For the MI analysis each missing datum is replaced by multiple values in multiple datasets. The imputed datasets are then analyzed and combined for inference. Since the primary efficacy, and secondary efficacy endpoints, are based on the same underlying data of change in VAS, and vary only in the parameterization (continuous VAS vs. dichotomized responder) or value used for the null hypothesis, the same imputed data sets will be used for the analysis of each endpoint. Imputation will be performed separately by treatment group.

Statistical Analysis Plan		Page 10 of 14
Sponsor SGX International	Study EU RCT DTM SCS vs. CMM	Version 3.0

For each imputation model, covariates will include:

- Baseline variables: age (years), gender, number of year(s) since diagnosed with chronic back pain, unilateral versus bilateral pain, back pain VAS
- Follow-up variables: end of trial phase back pain VAS, follow-up back pain VAS (after device activation) from 1 month through 24 months. The imputation models employed will correspond to the hypothesis being tested, for the primary and secondary endpoints through 6 months, the models will use data through 6 months. For secondary endpoints post 6 months, the model will be extended to the relevant time point.

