5.7.2.1 Handling of Missing Data

Since the two secondary endpoints are based on the same underlying VAS data as that for the primary efficacy endpoint, a similar treatment of handling missing data will be applied for the trial phase outcomes. In particular, for subjects who have a successful Trial Phase and planned to receive a permanent implant, VAS data used for the secondary endpoints will correspond to the results observed at the corresponding collection times (i.e. 1 month, 3 months, 6 months, 9 months, 12 months, 18 months, and 24 months). For subjects who do not have a successful Trial Phase (based on subject's pain score), the VAS data for the secondary endpoints will utilize the results from the end of the Trial Phase.

Subjects who were not able to complete the Trial Phase (e.g., an adverse event experienced during the Trial Phase, physician withdrawal due to non-compliance, withdrawal of consent, etc.) will be removed from the mITT analysis data set as no back VAS pain score is available at the End of Trial visit.

In the event of missing secondary endpoint data the primary analysis of the secondary endpoints will be conducted using multiple imputation instead of the methods specified above. The multiple imputed datasets from the primary endpoint analysis will also be used for the analysis of the secondary endpoints as described in Section 5.7.1.2. The same methods will be used for the responder endpoint evaluation at 1, 3, 9, and 12 months. The evaluation of mean change in VAS at 6 months will estimate the mean change and difference in means between groups along with the associated standard errors which will then be combined across imputations. The imputation model will be extended as needed for the evaluation of the secondary endpoint at 9, 12, 18, and 24 months.

As an additional supporting analysis, likelihood based repeated measures models will be used to produce estimates for the secondary endpoints in the presence of missing data.

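### The SAP gives no ITT outcome rule for test subjects who leave the Trial Phase without a score; under its no-imputation default, ITT would not test their exclusion

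*SAP*

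**What the plan says.** - **Sets.** SAP 5.2 defines ITT as all successfully randomized subjects who met the entry criteria, so test subjects who withdraw during the Trial Phase belong to it. The primary analysis uses mITT. On ITT, the section says only: "Supportive analyses will be performed for the Intent-to-Treat and Per-Protocol population".
- **Imputation.** SAP 5.7.1.2 applies multiple imputation to "missing primary endpoint data among the mITT subjects either randomized to control or DTM™ SCS subjects who did complete the Trial Phase". A test subject who withdraws during the Trial Phase meets neither condition.
- **Trial Failures.** SAP 5.7.1.2 and 5.7.2.1 carry the Trial Phase VAS forward for subjects whose trial was unsuccessful. This needs a score.
- **Unscored withdrawals.** SAP 5.7.2.1 says that subjects who could not complete the Trial Phase (adverse event, non-compliance, withdrawn consent) "will be removed from the mITT analysis data set as no back VAS pain score is available at the End of Trial visit". No sentence says what happens to them in ITT.
- **Default.** SAP 5.3 ends: "Unless otherwise specified, all other analyses will be based on the evaluable data with no imputation".
- **Protocol.** The synopsis defines the primary endpoint as a percentage of randomized subjects and adds: "Subjects who do not have a successful Trial Phase are considered failures (non-responders) toward the primary endpoint". Protocol B.7.2 is narrower. It ties an unsuccessful trial to the pain score, or to declining the implant because relief was insufficient.

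**The concern.** Only the test arm has a Trial Phase, so only the test arm can lose subjects because an End of Trial score is missing. The reasons the SAP lists, such as an adverse event, may well be related to outcome. mITT removes these subjects by design. The natural place to see the effect of that removal is ITT, where they are members. A programmer who finds no ITT rule and turns to the SAP 5.3 default would analyse only subjects with a VAS, and the withdrawals would disappear a second time.

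The ITT responder rate would then be conditional on having a score, although it would be labelled as a result for all randomized subjects. Agreement with mITT could be taken as reassurance about an exclusion that was never examined. If the rule is left open, it may also be chosen after the data are seen.

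**Working it through.** **1. The plan's own figure.** SAP section 4 gives: "Estimated responder rate of 60% in the test group and 30% in the control group"; "Significance level, alpha, of 0.05 two-sided"; "a sample size of 50 subjects in each group will result in greater than 85% power for the study". With pooled rate 0.45 and n = 50 per arm:
- SE under H0 = √(2 × 0.45 × 0.55 / 50) = 0.0995
- SE under H1 = √((0.6 × 0.4 + 0.3 × 0.7) / 50) = 0.0949
- Power = Φ((0.30 − 1.96 × 0.0995) / 0.0949) = Φ(1.107) = 86.6%

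The stated power reproduces. So does the number randomized: 100 / (1 − 0.33) = 149.3, or about 150, which is 75 per arm. No stated figure is in dispute.

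**2. Inputs for the illustration.**
- From the plan: 75 per arm; 60% and 30% response; Pearson chi-square without continuity correction.
- Assumed: w, the number of unscored test withdrawals. SAP section 4 gives only a combined 33% attrition, which also includes exits before 6 months.
- Assumed: everyone else has a usable score, and 22 of 75 controls respond (29.3%, the whole number just below 30%).

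**3. Formula.** For r test responders out of n: z = (r/n − 22/75) / √(p̄(1 − p̄)(1/n + 1/75)), where p̄ = (r + 22)/(n + 75). Evaluable-only uses n = 75 − w. Counting withdrawals as non-responders uses n = 75 with the same r.

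**4. One case in full (w = 10, r = 39).**
- Evaluable: p̄ = 61/140 = 0.436, SE = 0.0840, z = (0.600 − 0.293)/0.0840 = 3.65, p = 0.0003.
- All randomized: p̄ = 61/150 = 0.407, SE = 0.0802, z = (0.520 − 0.293)/0.0802 = 2.83, p = 0.005.

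**5. Results.**

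| w | Response among scored | Evaluable only | Withdrawals as non-responders |
|---|---|---|---|
| 10 | 60% | 39/65 = 60%, p = 0.0003 | 39/75 = 52%, p = 0.005 |
| 15 | 60% | 36/60 = 60%, p = 0.0003 | 36/75 = 48%, p = 0.019 |
| 20 | 60% | 33/55 = 60%, p = 0.0005 | 33/75 = 44%, p = 0.062 |
| 10 | 49% | 32/65 = 49%, p = 0.016 | 32/75 = 43%, p = 0.089 |

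At 60% response, the evaluable-only rate does not move with w. The all-randomized rate falls by 8 points at w = 10 and by 16 at w = 20. At w = 10 and w = 15 significance survives; at w = 20 it does not.

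**6. How firm the reversals are.** Both reversed cases lie near the threshold. If one of the 20 withdrawals were a responder (33 + 1), or two of the 10 (32 + 2), the result would be 34/75 = 45.3%, z = 2.03, p = 0.043.

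**7. Error rate.** Suppose the true rate over all randomized subjects is 30% in both arms and every withdrawal is a non-responder. The scored test subjects then respond at 0.30 × 75/(75 − w): 33.6% at w = 8 and 37.5% at w = 15. By exact binomial enumeration, the chance of a significant result favouring the test arm on evaluable data is 2.4% at w = 0, 6.2% at w = 8 and 15.5% at w = 15. With withdrawals counted as non-responders it stays at 2.4%.

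**The case against.** **The default may not govern ITT.** In SAP 5.3 the no-imputation sentence comes shortly after one on methods for the primary and secondary endpoints. The remaining analyses it refers to may therefore be those of other endpoints, and a supportive ITT run is still an analysis of the primary endpoint. This stands: no sentence assigns ITT to the default. But on that reading ITT has no rule at all for these subjects, and the same addition is needed.

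**The synopsis may already supply the rule.** The SAP is to be read with the protocol, and someone who withdraws mid-trial has not had a successful Trial Phase. This stands in part. Protocol B.7.2 defines lack of success by the pain score or by insufficient relief, which does not clearly reach an adverse event or withdrawn consent. The two places need reconciling.

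**ITT can differ from mITT.** A reader might infer that ITT merely repeats mITT and can check nothing. The documents do not support that. Under the literal definition in SAP 5.2, test subjects in mITT must have a successful Trial Phase, so scored Trial Failures are in ITT only, and ITT would test their exclusion. If primary data are missing, the primary mITT result comes from multiple imputation, which an evaluable-data ITT would not reproduce. ITT also drops subjects who failed entry criteria. None of this brings back the unscored withdrawals.

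**Other provisions.** SAP 5.3 promises sensitivity analyses for missing data, and SAP 5.4 reports exclusions with reasons, so the withdrawals would be visible. But the sensitivity analyses have no stated method or population, and a disposition table gives no effect estimate. The supporting repeated-measures model names no analysis set. If fitted to change from baseline, it gains nothing from subjects with no post-baseline value.

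**Non-responder status is one choice among several.** This stands. It is conservative for the test arm while missing controls would be imputed, which is why a tipping-point analysis belongs beside it.

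**Conclusion.** The gap is real. The SAP does not say how ITT handles test subjects without an End of Trial VAS. If the SAP 5.3 default is used, they leave the ITT denominator as they leave mITT, and ITT does not test that one-sided exclusion. It would also depart from the synopsis, which takes randomized subjects as the denominator.

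In the illustration, at 60% response, the ITT test-arm rate is 8 points higher with 10 withdrawals left out and 16 points higher with 20. Significance at 0.05 depends on the rule with 20 withdrawals at 60% response, and with 10 at about 49%. These sizes rest on assumed withdrawal counts, complete data otherwise, and no responders among the withdrawals.

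The matter ranks below the points that bear on the success criterion. Protocol B.7.3 and its Definition of Success rest on the primary test, which is run on mITT. ITT is supportive and cannot change the declared outcome.

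**What to change.** Add to SAP 5.7.1.2, before any outcome data are analysed:
- The no-imputation default in SAP 5.3 does not apply to the ITT analysis of the primary endpoint.
- Every ITT subject stays in the denominator.
- Test subjects without an End of Trial VAS are counted as non-responders, in line with the synopsis.
- Other missing 6-month scores in ITT are multiply imputed as for mITT.
- A tipping-point analysis varies the number of responders among the unscored withdrawals from none to all, and reports where the conclusion changes.

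Reconcile the synopsis, protocol B.7.2, SAP 5.2 and SAP 5.7.1.2 on two questions: whether a withdrawal without a score counts as an unsuccessful Trial Phase, and whether scored Trial Failures belong to mITT.

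The cost is SAP wording and one further table, with no new data. The sponsor should expect a less favourable supportive ITT responder rate in the test arm if there are unscored withdrawals.

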A multicenter feasibility study (NCT03110601) has also been completed in which DTM™ SCS programming approach was evaluated during the required period for trialing SCS therapy. In this acute study, 20 subjects completed a trial with DTM™ SCS and Conventional SCS programming approaches. In terms of back pain relief, the DTM™ SCS programming approach provided a mean of 68% pain relief and the Conventional SCS programming approach provided a mean of 43% pain relief, which translates to DTM™ SCS achieving 25% greater reduction than Conventional SCS. Notably with DTM™ SCS, 80% of subjects experienced 50% or better back pain relief, and 85% of the subjects preferred therapy received through the DTM™ SCS programming approach. The safety results were in line with expectations of previous SCS studies and the adverse events were mostly resolved within a few days with minimal interventions. There was one serious adverse event, epidural abscess, which although uncommon, is well established as a potential risk in SCS trials and was not related to either programming approach. There were no unanticipated adverse events.

The current study is a post-market, open-label, prospective, randomized, controlled multi-center study that will evaluate DTM™ SCS programming with CMM in comparison to CMM alone for chronic back pain sufferers with or without leg pain. This scientifically sound study will provide more information on safety, efficacy and health economic analytics for the DTM™ SCS programming approach.

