#### **B.5.5.1 Sample size rationale and statistical power**

The sample size estimate to determine primary endpoint is based on the primary objective of demonstrating superiority of the test group to the control group. Established methods were followed in determining the superiority criteria and the related sample size estimate

- Test basis: Pearson Chi-square binomial test for superiority
- Estimated responder rate of 60% in the test group and 30% in the control group
- Significance level, alpha, of 0.05 two-sided
- Randomization: 1:1
- A sample size of 50 subjects in each group will result in greater than 85% power for the study

Based on these assumptions, a minimum of 50 randomized subjects per treatment group (100 total) are required.

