- **Subjects randomized in the test group (DTM™ SCS with CMM)** will be scheduled for the trial stimulation phase, lasting approximately up to 30 days based on typical clinical practice of the site, to determine the subject's response to DTM™ SCS. Temporary or permanent leads and an external neurostimulator (ENS) will be used during this Trial Phase. Subjects will evaluate the therapy based on pain intensity under optimal DTM™ SCS parameters. Those who have a "successful Trial Phase" (defined as a 50% or greater pain reduction from Baseline in their back pain) will proceed to receive a permanent implant of leads and the internal neurostimulator (INS) and will undergo up to 24 months of stimulation delivery with assessments at 1, 3, 6, 9, 12, 18 and 24 months after the activation of the therapy. The implanted INS will be activated within 14 days after surgical procedure and DTM™ SCS therapy will be delivered for the next 24 months. Activation of the device marks the initial time point for effectiveness evaluation of the test study therapy after implantation. If needed, the investigator may attempt other SCS programming parameters available on Intellis™ neurostimulator to provide pain relief. If other parameters are effective, the parameters should be noted and analyzed. Assessments for pain intensity, use of medication and adverse events will be made at 1 month following Device Activation. At 3, 6, 9, 12, 18 and 24 months after Device Activation, subjects will be assessed for pain intensity, adverse events, extent of disability, use of medication, quality of life, health care utilization, Patient Global Impression of Change, and subject satisfaction. In addition, work status will be evaluated at 6, 12 and 24 months.
- **Subjects randomized in the control group (CMM alone)** will follow the best standard of care under CMM as prescribed by the Investigator i.e. optimized individual conventional therapy (see Section B.6.16). Randomization into the control group marks the initial time point for evaluation of the control study therapy. Subjects in the control group will also undergo up to 24 months of CMM with the same assessments as the test group at 1, 3, 6, 9, 12, 18 and 24 months after randomization.
- **Crossover:** Subjects randomized to either treatment group will have the possibility to crossover to the alternative treatment arm after the 6-month visit, if they meet all of the following criteria:
  - < 50% back pain relief from baseline;

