### **B.6.6. Test Arm: End of Trial Assessment**

At the end of the Trial Phase, subjects will be assessed for pain intensity under optimal therapy parameters. Anterior-posterior (AP) and lateral X-ray imaging will be done at the end of the Trial Phase. The subject will be assessed for adverse events and medication usage.

Those who have a "successful Trial Phase" (defined as a 50% or greater pain reduction from Baseline in their back pain) will proceed to permanent implantation of the SCS system to evaluate DTM™ SCS therapy, and permanent implantation of the Intellis™ SCS system will be scheduled. A threshold of 50% for the Trial Phase was predetermined as the minimum pain reduction that warrants consideration of a permanent implant and an opportunity to achieve a 50% pain reduction as defined in the Individual Subject Success criterion (see Section B.7.3).

Data from subjects who did not achieve 50% or greater pain reduction in back pain will not receive permanent implantation and will be carried forward toward the primary endpoint. These subjects will have the leads explanted and will exit the study. Following this exit, subjects will be followed by the Investigator at regular intervals, as dictated by standard of care at each site, in order to facilitate pain management. Any additional non-study related monitoring of the subject will be the responsibility of the subject's personal physician, as dictated by reasonable medical care.

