### B.8.1. Effectiveness

Results of the tests and standard questionnaires will be recorded in Case Report Forms at Baseline and during follow-up visits. Changes from Baseline will be calculated and compared between the two groups.

Effectiveness will be measured for each subject using the following tests:

- **Pain Visual Analog** The 10 cm visual analog scale (VAS) is a well validated and widely used scaled psychometric instrument to report pain severity. Subjects will score the severity of pain on a 10 cm line, with 0 indicating no pain and 10 indicating the worst pain imaginable. Subjects will complete a chronic back pain VAS in the clinic during scheduled study visits. Subjects will serve as their own control for the pain relief endpoint. Each subject's baseline pain score will be compared to the score at follow-up visits. Mean changes from baseline will be calculated for the entire cohort. The percentage of subjects who achieved  $\geq 50\%$  (back) pain relief will also be calculated based on VAS changes from baseline. VAS scores collected during the study visits will be used for the primary endpoint.

- [REDACTED]
- [REDACTED]
- [REDACTED]
- [REDACTED]

- [REDACTED]
- [REDACTED]
- [REDACTED]

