### **B.8.3. Health Economic Measures**

Costs and health outcomes (in terms of life-years and quality-adjusted life-years [QALYs]) associated will be captured from healthcare utilization data [REDACTED]

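### For disability, quality of life, global impression, satisfaction and healthcare use, failed-trial subjects vanish from the DTM arm, so trial responders are compared with unselected evaluable controls and the benefit is probably overstated

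*SAP*

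**What the plan says.** **Exit.** For a test subject with less than 50% back pain relief in the Trial Phase, Protocol B.6.6 states: "These subjects will have the leads explanted and will exit the study". The same section lists pain, adverse events, medication and X-rays at the end of the trial, and no questionnaire.

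**Timing of the other measures.** Protocol B.6.1 says that in the test arm, at 3 months after Device Activation and later, "subjects will be assessed for pain intensity, adverse events, extent of disability, use of medication, quality of life, health care utilization", together with global impression of change and satisfaction. Healthcare utilization starts at the visit 1 month after activation (Protocol B.6.9). Control subjects are assessed at visits dated from randomization (Protocol B.6.1, B.6.16).

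**Planned comparison.** Protocol B.8.1 says of the tests and questionnaires: "Changes from Baseline will be calculated and compared between the two groups". Protocol B.8.3 plans costs and QALYs from healthcare utilization data; the rest of that sentence is redacted.

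**Rule for trial failures.** SAP 5.7.1.2 says "results (i.e., VAS back scores) from the Trial Phase will be utilized for the primary endpoint" and attributes those scores to every later time point. SAP 5.7.2.1 does the same for the VAS secondary endpoints.

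**Default for everything else.** SAP 5.3: "Unless otherwise specified, all other analyses will be based on the evaluable data with no imputation". Protocol B.9.2.4 repeats this default and refers to the SAP for detail.

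**The concern.** A subject whose trial fails is never activated, so the test-arm schedule gives that subject no follow-up value for disability, quality of life, global impression, satisfaction or healthcare use. Nothing visible in the SAP fills the gap. The DTM side of these comparisons is then limited to subjects chosen by a response measured after randomization, while the control side has no matching filter. The supportive ITT analysis does not help: it restores the subjects but not their data. The plan meets this problem for VAS by keeping trial failures in, and has no visible counterpart for the other measures.

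At stake are secondary objectives: clinical effectiveness and health economics against CMM alone (Protocol B.2). The omitted subjects had lead placement and removal and did not reach the relief threshold.

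**Working it through.** **1. The plan's own figures.** Inputs from Protocol B.5.5.1: responder rates of 60% and 30%, 50 per group, "Significance level, alpha, of 0.05 two-sided". With a pooled rate of 0.45, z = [0.30 × √50 − 1.96 × √(2 × 0.45 × 0.55)] / √(0.6 × 0.4 + 0.3 × 0.7) = (2.121 − 1.379) / 0.671 = 1.107, so power is 86.6% (87.6% by exact enumeration of the Pearson test). This agrees with the stated figure of more than 85%. Attrition: 100 / (1 − 0.33) = 149.3, or about 150 randomized, 75 per arm. These figures concern the VAS responder endpoint and do not change. The documents give no effect size or power for the measures at issue.

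**2. Share of trial failures, f.** The documents give no separate rate. Protocol B.1 reports from the 20-subject feasibility study that "80% of subjects experienced 50% or better back pain relief"; borrowed as an assumption, this gives f = 20%. I show 10% to 33%. The 33% is the plan's combined attrition, which includes later exits, so it is an upper bound. Of 75 test subjects, 75 × (1 − f) = 67.5, 60 and 50.25 remain, or about 68, 60 and 50.

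**3. Overstatement factor.** Let D be the effect of DTM over CMM in trial responders and rD the effect in trial failures. Assume both groups would fare equally under CMM, and ignore other dropout.

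- All-randomized difference: (1 − f)D + f·rD
- Evaluable-only difference: D
- Factor: 1 / [(1 − f) + f·r]

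| r (effect in failures relative to responders) | f = 10% | f = 20% | f = 33% |
|---|---|---|---|
| −0.25 (worse than CMM) | 1.14 | 1.33 | 1.70 |
| 0 (no gain over CMM) | 1.11 | 1.25 | 1.49 |
| 0.5 (half the effect) | 1.05 | 1.11 | 1.20 |
| 1 (equal effect) | 1.00 | 1.00 | 1.00 |

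For example, at f = 20% and r = 0, 1 / 0.80 = 1.25. The same factor applies to a mean QALY gain.

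**4. If prognosis differs.** Suppose there is no treatment effect, and trial relief has correlation ρ with the later outcome. Keeping the top 1 − f on trial relief shifts the test mean by ρ·φ(c)/(1 − f) SD, where c is the f-quantile of the standard normal. At an assumed ρ = 0.3 the shift is 0.06, 0.10 and 0.16 SD. With SE = √(1/75 + 1/[75(1 − f)]) and the SD held at 1, a nominal two-sided 5% test would reject about 6%, 9% and 14% of the time. At ρ = 0 there is no shift. This is for scale only: the visible text names no test for these measures.

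**The case against.** **Redaction.** Protocol numbering jumps from B.7.4 to B.7.6 and from B.9.2.2 to B.9.2.4, parts of B.8.1 and B.8.3 are blacked out, and the columns of Table 1a cannot be read reliably. The SAP default applies only where nothing else is specified, so an unseen rule is possible. This stands as a limit on certainty. Still, the default itself is visible, Protocol B.9.2.4 defers to the SAP, and SAP 5.7.2.1 is followed by 5.8 with no overriding rule.

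**An exit visit.** Protocol B.6.21 lists trial failure as a reason for early withdrawal and implies a visit for subjects who have not withdrawn consent or been lost. Even if questionnaires were taken then, they would give no 6-month or later value.

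**Stronger readings that a reader might infer.**

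- *Every non-VAS comparison is affected.* It is not. Adverse events are captured from enrollment (Protocol B.8.2, Safety Measurements) and have an ITT sensitivity analysis (SAP 5.9). Medication is also recorded at the end of the trial.
- *The comparator is all controls.* The default also omits controls without data.
- *The benefit is certainly overstated.* The r = 1 row shows no bias when prognosis is equal. Overstatement is likely because trial response is the plan's own gate to implant, but it is not proven.
- *The costs of failed trials are lost.* The costing method is redacted, and SAP 5.4 counts unsuccessful trials and explants, so these procedures could be costed. The visible text does not say that they will be.

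**Baseline carry-forward.** It can err against DTM, since trial failures return to standard-of-care pain management. Assume improvements of 0.8 SD in responders and 0.2 SD both in failures and in controls. At f = 20% the true difference is 0.8 × 0.8 + 0.2 × 0.2 − 0.2 = 0.48 SD; carry-forward gives 0.8 × 0.8 + 0 − 0.2 = 0.44 SD. This objection stands. Baseline carry-forward should not be the only analysis.

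**Conclusion.** The point holds for disability, quality of life, global impression, satisfaction and healthcare use or QALYs. On the visible text, these comparisons are not comparisons of the groups as randomized, and they probably favour DTM SCS. If trial failures gain nothing over CMM, the factor is about 1.11 at 10% and 1.25 at 20% failures, with 1.49 at 33% as an upper bound. If they gain half the responders' effect, it is 1.05, 1.11 and 1.20. If they benefit equally and have the same prognosis, it is 1. Both f and r are assumptions.

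A reader might infer that the trial's main conclusion is at risk. This point does not support that. The primary endpoint is based on VAS and has its own trial-failure rule, and study success rests on that endpoint alone (Protocol B.8.2, Definition of Success). What is limited is what the trial can say on its secondary effectiveness and health-economic objectives.

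**What to change.** In SAP 5.3:

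1. Add an all-randomized analysis of these measures that keeps trial failures in the DTM arm under a stated assumption, for example the Baseline value carried forward, with a control-based multiple-imputation sensitivity analysis.
2. In the economic analysis, keep trial failures in the DTM arm with their trial and lead-removal costs.
3. Label the evaluable-only results *DTM trial responders versus evaluable controls* and draw no randomized between-arm conclusion from them alone.
4. Reconcile the mITT definition. SAP 5.2 admits only test subjects who successfully complete the Trial Phase, while SAP 5.7.1.2 attributes VAS scores to trial failures and removes from mITT only those who withdrew before completing the trial.

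Cost: SAP text and modest programming, with no new visits or subjects, because Baseline questionnaires are already collected. The downside is less favourable estimates and an untestable assumption for subjects who have left, which the sensitivity analysis addresses. If a redacted section already contains such a rule, a cross-reference in SAP 5.3 would do for that part.
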